a) Screening Visits: Eligible volunteers will have the study explained and provide informed consent according to the guidelines of the local Institutional Review Board for Human Research. A fasting blood profile for lipids, liver, renal and hematological function will be drawn. A 12-lead resting electrocardiogram (EKG) will be obtained and a medical history and physical examination performed. Height and weight will be measured using a standard physician's scale. Seated blood pressures will be measured in duplicate. Information on demographics and family medical history will be recorded. Subjects will complete the Mini Mental State Exam (MMSE) (60) and Center for Epidemiologic Studies Depression Scale (CES-D) questionnaires. Volunteers also will have a screening VO₂peak treadmill test as described below.

Table 1: Research Design		
	Time Duration	Research Activity
Phase 1	3 weeks	Screening & Enrollment
Phase 2	1 week	Baseline Testing
Phase 3	1 day	Randomization
Phase 4	2 weeks	Weight & Dietary Stabilization
Phase 5	1-2 months	Metabolic Pre Testing
Phase 6	6 months	TM+N or ST+N
Phase 7	1-2 months	Metabolic Post Testing

Baseline Testing (Phase 2): During this phase, subject will undergo a submaximal treadmill test, blood draw, and resting metabolic rate (RMR), as described below.

Randomization (Phase 3): Subjects are randomly assigned to either progressive 6 month treadmill aerobic exercise training 3 times per week plus nutritional modification or the reference control of education and stretch 2 times per week for 6 months plus nutritional modification.

Weight and Dietary Stabilization (Phase 4): Subjects will meet with a Registered Dietitian 2-3 times weekly for 2 weeks to learn "heart healthy" dietary patterns and ensure weight stabilization before metabolic testing. Details of the diet are described below. Prior to metabolic testing, subjects are asked to remain weight stable.

Metabolic Testing (Phase 5): This testing phase will occur over a period of 1-2 months for each individual. A VO₂peak treadmill test, body composition (anthropometrics, DXA, CT) tests, questionnaire completion, and functional and strength measures will occur during this phase. Subjects will be weight stabilized throughout the metabolic testing.

Treadmill Training plus Nutritional Modification versus Stretch Control plus Nutritional Modification (Phase 6):

Treadmill Training

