Peak: Treadmill tests will start at a self-selected pace, and will be advanced by adequate increments according to tolerance, perceived exertion, and medically credentialed clinician rating of gait stability. This clinically supervised test will determine treadmill gait safety, functional eligibility to participate (must walk 3 minutes at 0.1 MPH with handrail support), cardiopulmonary response to strenuous exertion defining exercise tolerance and safety, and allow us to pre-select testing parameters for subsequent constant velocity peak effort graded treadmill testing. Belt safety harness will be worn with a spotter behind the subject, and handrail support will be used at all times. Peak exercise tests will evaluate the cardiopulmonary response to exertion, under clinician supervision with continuous vital signs and EKG monitoring. Tests will be terminated at the subject's request, and based on American College of Sports Medicine criterion. Baseline peak test is reviewed by a cardiologist as part of our quality assurance program. The peak fitness test will be completed during Phase 1, Phase 5, and Phase 7.

Submaximal Treadmill Test: After a 12 hour fast, economy of hemiparetic gait will be measured using open circuit spirometry during a standard constant load submaximal effort treadmill walking task at a pre-established gait velocity (60-80% of self-selected floor walking velocity). This slower walking velocity is selected because untrained subjects with stroke usually cannot maintain their self-selected walking pace, precluding steady state measures of oxygen consumption that defines gait economy. The mean rate of VO₂ will be calculated based on the final 3 minutes of a 10-minute walk under steady state oxygen consumption conditions. Subjects not achieving a plateau in VO₂ will be re-tested at a lower velocity on a different date to eliminate potential confounding effects of fatigue on testing. This test will be completed before (Phase 3) and after (Phase 5) the Dietary Education (Phase 4), as well as in Phase 7 after the 6-month exercise or stretching interventions.

5. Energy Expenditure

Resting Metabolic Rate (RMR) will be measured using the ventilated hood technique while subjects lie quietly in bed for 30-45 mins under a clear plastic hood with expired air collected through a one-way valve (Weir JB deV. RMR will be measured at rest in Phase 3, 5 and 7.

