Activity Monitoring: Subjects will answer activity questionnaires. They will wear an accelerometer activity monitor on their belt for 5 to 7 days to determine caloric expenditure in daily activities in Phase 5 and Phase 7.

6. Dietary Intake Assessment: A Registered Dietitian will instruct subjects on how to complete a 3-5-day food record or collect 24 hour dietary recalls that will be analyzed and used as measures of dietary habits. Dietary assessment will occur in at the beginning and end of Phase 4, as well as in Phase 7 following the 6-month interventions.

Statistical Analysis and Expected Results: Data from the study will be entered into a data set and validated by the study PI. Initially, analyses will be adjusted for site to determine whether site is a significant covariate to our outcomes of interest; however, if site is not significant, it will be dropped from further analyses. Descriptive statistics will be calculated for all variables using SAS version 9.3 (SAS Institute, Cary, N.C.) and the R statistical package. Exploratory data analyses will be performed to check the data for extreme values and to determine the distribution of values. Extreme values will be verified against original source documents. When necessary, data will be transformed to normality using appropriate transforms. A two-tailed P <0.05 will considered indicative of a significant result. In addition to P values, 95% confidence intervals will be reported. The primary variable of interest to test the main hypotheses includes: 1) total daily energy expenditure measured by RMR (indirect calorimetry) + energy expenditure during activity (accelerometry). Secondary variables include substrate oxidation measured as fat and glucose oxidation during submaximal exercise, systemic (plasma) oxidative stress, VO₂peak.

Statistical Analysis Plan

Primary Aim: To assess the effects of six months of TM+N versus ST+N on total daily energy expenditure (primary outcome) and substrate oxidation in chronic stroke survivors.

Expected Results: We anticipate that TM+N will result in significant changes in RMR and energy expenditure during activity, as well as greater reliance on fat at resting and an improved ability to switch from fat to carbohydrate utilization during submaximal exercise and after a mixed meal challenge.

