Aim 2: To examine the effects of six months of TM+N versus ST+N on systemic and tissue inflammation and oxidative stress and antioxidant capacity in chronic stroke survivors.

Expected Results: We expect that TM+N will result in decreased oxidative stress in the circulation.

The change (post-pre) value of the energy expenditure and substrate oxidation outcomes, along with measures of oxidative stress and antioxidant capacity will be the dependent (outcome) variables in a series of ANOVAs (one for each outcome variable). Independent variables will include the initial value of the outcome variable, group assignment, along with the subject's age and BMI, and if needed (i.e. if there are differences between the exercise and stretching subjects) medications and medical conditions other than presence of stroke. Baseline dietary intake will be treated as covariates. These analyses will tell us if there is a differential effect of exercise versus stretch control with nutritional modification on the outcome measures.

References:

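### RMR and substrate oxidation each have two pre-training values, but the model adjusts for one initial value tied to no phase; entering both as covariates removes the choice

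*Combined protocol and SAP*

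**What the plan says.** The Statistical Analysis Plan takes the post-minus-pre change as the dependent variable for energy expenditure, substrate oxidation, oxidative stress and antioxidant capacity. On adjustment it says "Independent variables will include the initial value of the outcome variable", alongside group, age, BMI and other covariates. Neither the pre value nor the initial value is tied to a phase.

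The measurement schedule gives more than one candidate:

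- **RMR** (Study Procedures, Energy Expenditure): "RMR will be measured at rest in Phase 3, 5 and 7".
- **Submaximal test** (Study Procedures, Treadmill Tests): "This test will be completed before (Phase 3) and after (Phase 5) the Dietary Education (Phase 4", and again in Phase 7. The statistical section derives fat and glucose oxidation from this test.
- **First occasion, stated differently**: the Baseline Testing (Phase 2) paragraph says "subject will undergo a submaximal treadmill test, blood draw, and resting metabolic rate (RMR" will be done there, not in Phase 3.
- **Accelerometry** (Activity Monitoring): worn "to determine caloric expenditure in daily activities in Phase 5 and Phase 7", so it has one value before training.

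The primary outcome, TDEE, is RMR plus accelerometer-based activity expenditure. Randomization is Phase 3. The diet phase (Phase 4) and Phase 5 testing both come after it.

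**The concern.** With two pre-training values, one change score and one baseline covariate, an analyst can construct more than one version of the same model, and each can be defended from the text. If the version is settled after results are seen, the nominal 5% error rate no longer holds.

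TDEE has a further problem. Accelerometry exists only in Phase 5 before training, so a pre value built with the earlier RMR would add components measured on either side of the diet phase.

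The model also leaves out a measurement that the schedule already collects and that may predict the outcome. The earlier value matters for another reason: if it is taken in Phase 2, it is the only one of the two obtained before allocation.

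**Working it through.** **1. Inputs.** The measurement phases, the 1:1 allocation and the two-sided 0.05 level come from the document. It gives no sample size, standard deviation, effect size or test-retest correlation, so there is no plan figure to reproduce. Every correlation r, variance share and number per arm below is an assumption.

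**2. Which phase is meant?**

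| Points to Phase 5 | Points to the earlier value |
|---|---|
| Table 1 labels Phase 5 as pre testing | The covariate is called the initial value |
| The phase overview places Phase 4 before baseline research testing | Phase 2 is titled baseline testing |
| Phase 7 repeats the Phase 5 tests | RMR and the submaximal test are listed under Phase 2; the Phase 5 paragraph names neither |

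The balance favours Phase 5, but the analysis section does not settle it.

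**3. Cost of choosing late.** Null simulation with 20,000 runs per setting and equal correlations r among the two pre values and the post value. The post value is regressed on group and one pre value, and the smaller of the two p-values is kept. Rejection rate at 0.05:

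| r | 20 per arm | 40 per arm |
|---|---|---|
| 0.5 | 0.074 | 0.075 |
| 0.7 | 0.083 | 0.084 |
| 0.8 | 0.090 | 0.087 |
| 0.9 | 0.090 | 0.087 |

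Each single-baseline analysis on its own stayed between 0.048 and 0.053.

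**4. Why two covariates remove the choice.** Let E be the earlier value, F the Phase 5 value, Y the post value and G the group. If Y − F = a + bG + cE + dF + error, then adding F − E to both sides gives Y − E = a + bG + (c − 1)E + (d + 1)F + error. The group coefficient b, its standard error and its p-value are unchanged.

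This does not carry over to TDEE when the covariates are Phase 5 TDEE and the earlier RMR. A hybrid pre value (earlier RMR plus Phase 5 activity) is not a linear combination of those two covariates. The pre value of TDEE therefore has to be fixed explicitly.

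**5. Precision, equal correlations.** Residual variance is 1 − r² with one baseline and 1 − 2r²/(1 + r) with two. The ratio is (1 + 2r)/(1 + r)².

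- r = 0.5: 2.0/2.25 = 0.889, an 11.1% reduction
- r = 0.7: 2.4/2.89 = 0.830, 17.0%
- r = 0.8: 2.6/3.24 = 0.802, 19.8%
- r = 0.9: 2.8/3.61 = 0.776, 22.4%

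The standard error falls by 5.7% to 11.9% across this range.

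**6. Precision, earlier value weaker.** Let p be the correlation of F with Y, q that of E with Y, and t that of E with F. Residual variance with both is 1 − (p² + q² − 2pqt)/(1 − t²).

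- p = 0.7, q = 0.6, t = 0.7: 1 − 0.262/0.51 = 0.486, against 0.51 for Phase 5 alone; ratio 0.953, a 5% saving
- p = 0.7, q = 0.49, t = 0.7: ratio 1.00, no saving

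Over the seven cases tried, the saving was 0% to 5%. Using the simple mean of E and F instead ranged from 1% better to 18% worse than Phase 5 alone.

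**7. Precision, TDEE.** Only RMR has a second value. Assume independent components, RMR carrying share s of the variance, and correlations r_R (RMR, any two occasions) and r_A (activity). Example with s = 0.5, r_R = 0.8, r_A = 0.5:

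- Covariance of pre and post TDEE = 0.5 × 0.8 + 0.5 × 0.5 = 0.65, so residual variance is 1 − 0.65² = 0.5775.
- Earlier RMR has variance 0.5 and covariance 0.4 with both pre and post TDEE. Adding it gives 1 − (0.5 × 0.65² − 2 × 0.4 × 0.65 × 0.4 + 0.4²)/(0.5 − 0.4²) = 1 − 0.16325/0.34 = 0.520.
- The saving is 1 − 0.520/0.5775 = 10.0%.

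Over s = 0.25 to 0.75, r_R = 0.7 to 0.9 and r_A = 0.5 to 0.8, the savings ran from 2.1% to 17.2%.

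**The case against.** The strongest reply is that the plan does have a guide. Table 1, the phase overview and the Phase 7 text all lean towards Phase 5, so leaving the phase unnamed is a gap in detail. That stands, and naming the phase would on its own be a small correction.

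A second reply is that the choice barely changes what is estimated. Both arms receive the Phase 4 diet instruction. If the same value is subtracted and adjusted for, the group coefficient equals that from modelling the post value, so only the covariate differs. This also stands, and it answers a reader who infers that using the earlier value would contaminate the treatment contrast with the diet period. It does not cover the mixed reading, in which the Phase 5 value is subtracted while the earlier one is the covariate. Nor does it restore the error rate if the choice is made late.

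Third, a reader might infer that the plan throws away a sure 11% to 22% of precision, or the equivalent number of participants. The documents do not support this. The two values straddle a diet change, participants without a VO₂ plateau are retested at a lower speed, the earlier value lies further from Phase 7, and the model already adjusts for age, BMI and dietary intake.

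Fourth, a reader might add VO₂peak, since "The peak fitness test will be completed during Phase 1, Phase 5, and Phase 7". It is a secondary variable, but it is absent from the outcomes listed for the change-score model. The peak-test text also gives eligibility, safety and set-up purposes, including to "allow us to pre-select testing parameters for subsequent constant velocity peak effort graded treadmill testing", so the Phase 1 screening test is not clearly a replicate. It is left out here.

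Finally, Phase 5 is not a clean baseline, because it follows randomization. That is correct, and the fix has to allow for it. It does not show that Phase 5 values differ by arm, and the documents hold no data on that.

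**Conclusion.** The point holds for RMR and substrate oxidation, and for the RMR component of TDEE. Each has two pre-training values, and the model uses one without saying which. The text leans towards Phase 5 without settling it.

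A choice made after seeing results would raise two-sided type I error from 0.05 to about 0.07 to 0.09, under assumed correlations of 0.5 to 0.9 and 20 or 40 per arm. Nothing in the documents suggests that such a choice was intended.

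The precision gain is possible, not assured. It is 11% to 22% of residual variance with equal correlations, 0% to 5% if the earlier value is the weaker predictor, and 2% to 17% for TDEE, all on assumed inputs. It would be wrong to infer that the primary outcome has two complete baselines; Phase 5 is the only pre-training phase with accelerometry.

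The change should be made, mainly because it closes the choice at little cost.

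**What to change.** Before outcomes are compared by arm, amend the Statistical Analysis Plan as follows.

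1. For RMR and each substrate-oxidation outcome, enter the earlier value and the Phase 5 value as two separate covariates. Do not use their simple mean.
2. For TDEE, define pre as Phase 5 RMR plus Phase 5 activity expenditure, and add the earlier RMR as a further covariate.
3. Reconcile Phase 2 with Phase 3 for the first RMR and submaximal tests, so that they clearly precede allocation.
4. Because Phase 5 follows randomization, add a sensitivity analysis that adjusts only for the pre-randomization value where one exists. For TDEE this is available for the RMR component only.
5. For blood outcomes, name the phase in which the pre-training draw is actually scheduled. A draw is listed in Phase 2, the Phase 5 paragraph names none, and the blood-analysis section gives no phase.
6. State how a missing earlier value is handled, so that the added covariate does not remove participants.

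The cost is SAP wording and one degree of freedom per model. On the Study Procedures schedule, no new data are needed.
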